9.3 Agent Inventory Records

The investigator, or a responsible party designated by the investigator, must maintain a careful record of the receipt, dispensing and final disposition of all agents using the appropriate (Drug) Accountability Record form (DARF) available on the CTEP forms page. Store and maintain separate NCI Investigational Agent Accountability Records for each agent, strength, formulation and ordering investigator on this protocol.

9.3.1 Investigator Brochure Availability:

The current version(s) of the IB for the agent will be accessible to site investigators and research staff through the PMB Online Agent Order Processing (OAOP) application. Access to OAOP requires the establishment of a CTEP Identity and Access Management (IAM) account and the maintenance of an “active” account status, a “current” password and active person registration status. Questions about IB access may be directed to the PMB IB coordinator via email.

9.3.2 Useful Links and Contacts:

- CTEP Forms, Templates, Documents: <http://ctep.cancer.gov/forms/>
- NCI CTEP Investigator Registration: [contact]
- PMB policies and guidelines: http://ctep.cancer.gov/branches/pmb/agent_management.htm
- PMB Online Agent Order Processing (OAOP) application: <https://ctepcore.nci.nih.gov/OAOP/>
- CTEP Identity and Access Management (IAM) account: <https://ctepcore.nci.nih.gov/iam/>
- CTEP IAM account help: [contact]
- PMB email: [contact]
- IB Coordinator: [contact]
- PMB phone and hours of service: [contact] Monday through Friday between 8:30 am and 4:30 pm (ET)

10.0 CRITERIA FOR REMOVAL FROM PROTOCOL THERAPY AND OFF STUDY CRITERIA

10.1 Criteria for Removal from Protocol Therapy

- a) Clinical (including physical examination or serum tumor markers) or radiographic evidence of progressive disease (See [Section 12](#))
- b) Adverse Events requiring removal from protocol therapy (See [Section 13](#)).
- c) Refusal of protocol therapy by patient/parent/guardian
- d) Non-compliance that in the opinion of the investigator does not allow for ongoing participation.
- e) Completion of 26 cycles of therapy.
- f) Physician determines removal from protocol is in the patient's best interest.
- g) Repeat eligibility studies are outside the parameters required for eligibility prior to the start of cycle 1 BAY 1895344 (elimusertib) (See [Section 4.0](#)).
- h) Study is terminated by Sponsor.
- i) Pregnancy
- j) Development of secondary malignancy

Patients who are removed from protocol therapy during Cycle 1 should continue to have the required observations in [Section 8.1](#) until the originally planned end of the cycle or until all adverse events have resolved per [Section 13.5](#) whichever happens LATER. The only exception is with documentation of the patient's withdrawal of consent. Patients who are removed from protocol therapy in subsequent cycles should have the necessary observations to ensure adequate clinical care.

Patients who are off protocol therapy are to be followed until they meet the criteria for Off Study ([see Section 10.2](#)). Ongoing adverse events, or adverse events that emerge after the patient is removed from protocol therapy, but within 30 days of the last dose of investigational agent, must be followed and reported via RAVE and CTEP-AERS (if applicable). Follow-up data will be required unless consent is withdrawn.

10.2 Off Study Criteria

- a) The fifth anniversary of the date the patient was enrolled on this study.
- b) Withdrawal of consent for any required observations or data submission.
- c) The patient does not receive protocol treatment after study enrollment.
- d) Patient enrollment onto another COG study with therapeutic (anti-cancer) intent.
- e) Lost to follow-up
- f) Death.

11.0 STATISTICAL AND ETHICAL CONSIDERATIONS

11.1 Sample Size and Study Duration

Dose escalation (Part A) will require a minimum of 4 DLT-evaluable patients and a maximum of 12. Once the MTD or recommended Phase 2 dose has been defined, up to 6 additional patients with recurrent or refractory solid tumors without restrictions on heme evaluability may be enrolled to acquire PK data in a representative number of young patients (i.e. patients < 12 years old). Therefore, a maximum of 23 patients is anticipated for Part A allowing for 2 dose levels, PK expansion, and 20% inevaluability. Review of the enrollment rate into previous COG early phase new agent studies indicates that 1-2 patients per month are available, which will permit completion of the study within 12-23 months.

In the unlikely event that both dose levels are expanded to 12 patients each (see [section 11.2.2](#)), the absolute maximum number of patients enrolled in Part A will be 38 which would require up to 38 months accounting for 2 dose levels, PK expansion, and 20% inevaluability.

The three disease-specific phase 2 cohort studies will require a minimum of 20 response-evaluable patients. The maximum number of patients will be 67 allowing for 20% inevaluability. This part of the study is expected to be completed within about 25 months assuming 1 patient per month per cohort is available. However, completion of enrollment to Part B3 (DDR) will not be required for termination of the study.

Overall, this study will plan to enroll up to 90 patients within 48 months.

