4.1.11 Organ Function Requirements

4.1.11.1 Adequate Bone Marrow Function Defined As:

a. For patients with solid tumors without known bone marrow involvement

- Peripheral absolute neutrophil count (ANC) $\geq 1000/\text{uL}$
- Platelet count $\geq 100,000/\text{uL}$ (transfusion independent, defined as not receiving platelet transfusions for at least 7 days prior to enrollment)
- Hemoglobin $\geq 8.0 \text{ g/dL}$ at baseline (may receive RBC transfusions)

b. Patients with known or possible bone marrow metastatic disease will be eligible for study provided they meet the blood counts in [4.1.11.1.a](#) (may receive transfusions provided they are not known to be refractory to red cell or platelet transfusions). These patients will not be evaluable for hematologic toxicity. At least 5 of every cohort of 6 patients must be evaluable for hematologic toxicity for the dose-escalation part of the study. If dose-limiting hematologic toxicity is observed, all subsequent patients enrolled must be evaluable for hematologic toxicity.

4.1.11.2 Adequate Renal Function Defined As:

- Serum creatinine clearance or radioisotope GFR $\geq 70 \text{ mL/min}/1.73 \text{ m}^2$ or
- A creatinine based on age/gender as follows:

Age	Maximum Serum Creatinine (mg/dL)	
	Male	Female
1 to < 2 years	0.6	0.6

THIS PROTOCOL IS FOR RESEARCH PURPOSES ONLY, SEE PAGE 1 FOR USAGE POLICY

2 to < 6 years	0.8	0.8
6 to < 10 years	1	1
10 to < 13 years	1.2	1.2
13 to < 16 years	1.5	1.4
≥ 16 years	1.7	1.4

The threshold creatinine values in this Table were derived from the Schwartz formula for estimating GFR³⁹ utilizing child length and stature data published by the CDC.

4.1.11.3 Adequate Liver Function Defined As:

- Bilirubin (sum of conjugated + unconjugated or total) $\leq 1.5 \times$ upper limit of normal (ULN) for age.
- SGPT (ALT) ≤ 135 U/L. For the purpose of this study, the ULN for SGPT is 45 U/L.

4.1.11.4 Adequate Neurologic Function Defined As:

- Patients with seizure disorder may be enrolled if on anticonvulsants and well controlled as evidenced by no increase in seizure frequency in the prior 7 days. For patients a history of seizure but not on anticonvulsants, no seizure in the past 3 months. If needed, evaluate use of enzyme-inducing anticonvulsants as stated in [Section 4.2.2](#).
- Nervous system disorders (CTCAE v5) resulting from prior therapy must be \leq Grade 2, with the exception of decreased tendon reflex (DTR). Any grade of DTR is eligible.

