11.2 Definitions

11.2.1 Evaluable for Adverse Events:

Any patient who receives at least one dose of BAY 1895344 (elimusertib) or who experiences a dose-limiting toxicity is considered evaluable for Adverse Events. In addition, during Cycle 1, patients not experiencing a DLT must receive at least 75% of the prescribed dose per protocol guidelines and must have the appropriate toxicity monitoring studies performed to be considered evaluable for dose limiting toxicity. Patients who do not have DLT and are not considered evaluable for dose limiting toxicity in Part A will be replaced.

11.2.2 Maximum Tolerated Dose:

- The MTD will be the maximum dose at which fewer than one-third of patients experience DLT (See [Section 5.5](#)) during Cycle 1 of therapy.
- In the unlikely event that two DLTs observed out of 6 evaluable patients are different classes of Adverse Effects (eg, hepatotoxicity and myelosuppression), AND all of the following conditions are met, expansion of the cohort to 12 patients will be considered:
 - One of the DLTs does not appear to be dose-related
 - The Adverse Effects are readily reversible
 - The study chair, PEP-CTN statistician, PEP-CTN committee chair or vice chair, and IND sponsor all agree that expansion of the cohort is acceptable

If fewer than 1/3 of patients in the expanded cohort experience dose-limiting toxicities, the dose escalation can proceed.

- The DLTs observed in the pharmacokinetic (PK) expansion cohort will contribute towards the total number of DLTs observed at the RP2D/MTD during the dose escalation portion of the

study. If $\geq 1/3$ of the cohort of patients at the RP2D/MTD (during the dose escalation plus the PK expansion) experience DLT then the MTD will be exceeded.

- If required number of responses per the Simon two-stage design for expansion is not met for either the ARMS or EWS phase 2 cohorts whilst the PK expansion is still enrolling, the PK expansion will subsequently be closed to those patients.

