11.8 Evaluability for Toxicity

All patients who experience DLT or receive at least at least 75% of the planned dose of BAY 1895344 (elimusertib) during cycle 1 according to protocol guidelines will be evaluable for toxicity.

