12.2.1 Definitions**12.2.1.1 Evaluable for toxicity:**

All patients who experience a cycle 1 DLT or receive at least 75% of the planned dose will be evaluable for toxicity from the time of their first treatment with BAY 1895344 (elimusertib). Enrolled patients who have not received any treatment will not be considered evaluable for toxicity.

12.2.1.2 Evaluable for objective response:

All patients who receive at least one dose of BAY 1895344 (elimusertib) will be evaluable for response. Evaluable patients who demonstrate a complete or partial response confirmed by central review before receiving non-protocol anti-cancer therapy will be considered a responder. All other evaluable patients will be considered non-

responders. The evaluation period for determination of the best response will be 6 treatment cycles. All patients considered to have a response (CR or PR) must have imaging studies reviewed centrally. Centers will be notified by the PEP-CTN about requests for scans of patients with CR, PR, or long-term stable disease. See [Section 8.4](#) regarding shipping instructions.

12.2.1.3 Evaluable Non-Target Disease Response:

Eligible patients who have lesions present at baseline that are evaluable but do not meet the definitions of measurable disease and have received at least one dose of protocol therapy will be considered evaluable for non-target disease. The response assessment is based on the presence, absence, or unequivocal progression of the lesions.

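### The pooled one-third dose re-check counts PK-expansion patients who cannot be scored for hematologic DLT, so it can keep a dose that the hematologically evaluable patients would reject

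*Combined protocol and SAP*

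**What the plan says.** Section 4.1.11.1.b admits patients with known or possible marrow disease but states: "These patients will not be evaluable for hematologic toxicity". It limits them in two ways. The first is a floor confined to escalation: "At least 5 of every cohort of 6 patients must be evaluable for hematologic toxicity for the dose-escalation part of the study". The second has no such confinement: "If dose-limiting hematologic toxicity is observed, all subsequent patients enrolled must be evaluable for hematologic toxicity".

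Section 11.1 opens the PK expansion: "up to 6 additional patients with recurrent or refractory solid tumors without restrictions on heme evaluability may be enrolled to acquire PK data". Section 11.2.2 adds the DLTs seen there to those from escalation. Its re-check says that if at least one third "of the cohort of patients at the RP2D/MTD (during the dose escalation plus the PK expansion) experience DLT then the MTD will be exceeded".

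Three places define who counts. Section 11.2.1: "patients not experiencing a DLT must receive at least 75% of the prescribed dose per protocol guidelines", together with the required monitoring. Section 11.8: "All patients who experience DLT or receive at least at least 75% of the planned dose of BAY 1895344 (elimusertib) during cycle 1". Section 12.2.1.1: "All patients who experience a cycle 1 DLT or receive at least 75% of the planned dose will be evaluable for toxicity". None mentions hematologic evaluability. Section 2.5.2 puts the RP2D criterion in terms of evaluable patients (under 33% with a DLT), but nothing in the plan defines evaluable so as to leave marrow patients out.

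**The concern.** A marrow patient who takes at least 75% of the Cycle 1 dose enters the denominator of the re-check as a patient without DLT, although hematologic toxicity cannot be scored in that patient. Section 5.2.1 names hematologic toxicity as the drug's most common toxicity, so the dilution falls on the events that matter most.

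The decision at stake is the dose given to patients under 18 in Part B. Under 11.1, escalation may rest on as few as 4 DLT-evaluable patients. The pooled one-third rule is then the only numerical re-check of that dose, because the stopping rules in 11.5 concern response alone. The error runs one way, toward keeping a dose that is too high.

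**Working it through.** **The plan's own figures.** Part A maximum: (12 + 6)/0.8 = 22.5, rounded up to 23. Absolute maximum: (24 + 6)/0.8 = 37.5, rounded up to 38. Both reproduce, so the plan does count 6 expansion patients.

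**Counts that need no assumed rates.**
- Escalation 1/6 with a non-hematologic DLT; then 3 marrow patients with no scored DLT and 3 evaluable patients with 2 hematologic DLTs. Rule as written: 3/12 = 25%, dose kept. Hematologically evaluable patients: 3/9 = 33.3%, MTD exceeded.
- Escalation 0/4; then 2 marrow patients with no scored DLT and 4 evaluable patients with 3 hematologic DLTs. As written: 3/10 = 30%, kept. Evaluable: 3/8 = 37.5%, exceeded.

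The smallest number of marrow patients that can flip the decision at 3 DLTs is three in a 6+6 cohort (3/9), two in 5+6 (3/9) and one in 4+6 (3/9).

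**Assumptions for probabilities.** The documents give neither the pediatric DLT rate p nor the number k of marrow patients among the 6. I take p = 0.40. For the hematologic share h of DLTs I take 5/6: in the adult table in 2.3.2, 5 of the 6 patients with DLT had hematologic events, all at 60 to 80 mg and under different DLT rules. I also show h = 1/2. All escalation patients are taken as hematologically evaluable.

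**Model.** DLTs in evaluable expansion patients: a ~ Bin(6−k, p). Scorable DLTs in marrow patients: b ~ Bin(k, p(1−h)). With x0 DLTs in n0 escalation patients, the rule fires if x0 + a + b ≥ (n0 + 6)/3. A second test in hematologically evaluable patients would also fire if x0 + a ≥ (n0 + 6 − k)/3.

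**Start 1/6** (3 more DLTs needed).
- k = 0: P(Bin(6, 0.4) ≥ 3) = 45.6%.
- k = 3, 11.1 overrides: P(a=3) + P(a=2)P(b≥1) + P(a=1)P(b≥2) + P(a=0)P(b=3) = 0.064 + 0.288×0.187 + 0.432×0.0127 + 0.216×0.0003 = 12.3%.
- k = 3, post-DLT sentence governs: with probability h the escalation DLT was hematologic, so no marrow patient may enroll. Hence 5/6 × 45.6 + 1/6 × 12.3 = about 40.0%.

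Chance (%) that the dose is rejected, p = 0.40, start 1/6:

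| k | 0 | 1 | 2 | 3 | 4 | 5 | 6 |
|---|---|---|---|---|---|---|---|
| h = 5/6, sentence governs | 45.6 | 43.6 | 41.7 | 40.0 | 38.8 | 38.3 | 38.1 |
| same, plus second test | 45.6 | 43.6 | 41.7 | 43.9 | 40.8 | 38.3 | 38.1 |
| h = 5/6, 11.1 overrides | 45.6 | 34.0 | 22.5 | 12.3 | 5.1 | 1.7 | 0.5 |
| h = 1/2, sentence governs | 45.6 | 42.1 | 38.7 | 35.3 | 32.3 | 29.8 | 27.7 |
| same, plus second test | 45.6 | 42.1 | 38.7 | 42.7 | 35.6 | 29.8 | 27.7 |

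The second test adds at most 43.9 − 40.0 = 3.9 points at h = 5/6 and 42.7 − 35.3 = 7.4 at h = 1/2. The governing rows ignore any guard triggered inside the expansion, so they are pessimistic.

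**Clean starts (0/4, 0/5 or 0/6).** Four of 6 new DLTs are needed. Full evaluability gives P(Bin(6, 0.4) ≥ 4) = 17.9%. With the sentence in force, let each candidate be a marrow patient with probability q until a hematologic DLT is seen, with results known at once. At h = 5/6 the rule fires in 14.2% (q = 1/4) or 10.0% (q = 1/2). With the second test at q = 1/2 it fires in 18.1% from 0/4, 12.4% from 0/5 and 10.4% from 0/6. If 11.1 overrides, three marrow patients give 1.6%.

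**False alarms**, p = 0.20, h = 5/6, start 1/6, sentence in force plus second test, k = 0 to 6: 9.9, 9.3, 8.9, 10.0, 8.9, 8.3, 8.3%. Full evaluability gives P(Bin(6, 0.2) ≥ 3) = 9.9%.

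**The case against.** The strongest reply is that the plan already contains the guard. Section 4.0 requires eligibility criteria to be applied literally and without waiver, and 4.1.11.1.b is such a criterion. Its 5-of-6 floor is confined to escalation; the post-DLT sentence is not. Section 11.1 is sample-size text. Read together, 11.1 lifts the floor and leaves the sentence standing. I accept this as the more natural reading, although the phrase in 11.1 is broad enough that the plan should say so.

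Second, the dilution is partial. Marrow patients must meet the same entry counts, and missing more than one weekly block is a DLT under 5.2.1 and 5.5.2. If half of their hematologic events surfaced that way, the k = 3 figure from 1/6 would be 42.7% with the sentence in force, or 28.5% without it.

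Third, these probabilities are conditional on the start. At p = 0.40, exactly one DLT in 6 has probability 6 × 0.4 × 0.6^5 = 18.7%, so the unconditional loss by that path at k = 3 is about 0.187 × 5.6 = 1.0 percentage point.

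Fourth, other oversight exists: DLT reports within 24 hours (5.4), dose reduction (6.1.1), weekly review (14.5.2) and a DSMC meeting at least every 6 months (14.5.1). This stands for individual safety, but none of it sets a numerical rule for the dose. Relaxing hematologic evaluability to obtain PK data in young children is also a legitimate choice; the point concerns only the denominator.

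A reader might go further and infer that the re-check is close to disabled, citing 12.3% from 1/6 or 1.6% from a clean start. Those figures need 11.1 to override an eligibility sentence, which the documents do not say.

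**Conclusion.** The point holds in a limited form. As written, 11.2.2 can keep a dose at 3/12 or 3/10 that the hematologically evaluable patients would reject at 3/9 or 3/8, and the reference to evaluable patients in 2.5.2 does not prevent this. If the post-DLT sentence applies, both examples need the marrow patients to enroll before the first hematologic DLT is known.

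On that reading the loss from 1/6 with three marrow patients is about 5.6 points (45.6% to 40.0%) at h = 5/6 and about 10 points (to 35.3%) at h = 1/2. After a clean escalation the check is weak in any case, at 17.9% with full evaluability, and falls to 14.2% or 10.0% for q = 1/4 or 1/2. All probabilities rest on the assumed p, h, and k or q; the count examples do not. I would put this to the sponsor as a change to consider.

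**What to change.** 1. In 11.2.2, replace the re-check criterion with: *The MTD is exceeded if at least 1/3 of the pooled DLT-evaluable patients at the RP2D/MTD (dose escalation plus PK expansion), or at least 1/3 of those pooled patients who are evaluable for hematologic toxicity, experience DLT.* Keeping the first limb means that a non-hematologic DLT in a marrow patient still counts.
2. In 11.1, after the PK-expansion wording, add: *except that once a dose-limiting hematologic toxicity is observed, all subsequent patients must be evaluable for hematologic toxicity (4.1.11.1.b).* On the natural reading this only confirms an existing rule, but it closes off the reading that gives 12.3%.

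Sections 5.2.1 and 5.5.2 can stay as they are.

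With the sentence in force, the first edit helps mainly after a clean 0/4 escalation (10.0% to 18.1% at q = 1/2). Elsewhere it adds about 0 to 4 points, or up to about 7 if only half of DLTs are hematologic. It does not cure the weakness after 0/6.

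No patients or procedures are added. False alarms at a 20% DLT rate from 1/6 run at 8.3 to 10.0%, about the 9.9% of full evaluability; the highest value is 11.6% if one escalation patient was also not hematologically evaluable. PK accrual may slow after a hematologic DLT. A marrow patient sent to Part B instead would need measurable disease and would give 6 required PK samples rather than 12.

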11.2 Definitions

11.2.1 Evaluable for Adverse Events:

Any patient who receives at least one dose of BAY 1895344 (elimusertib) or who experiences a dose-limiting toxicity is considered evaluable for Adverse Events. In addition, during Cycle 1, patients not experiencing a DLT must receive at least 75% of the prescribed dose per protocol guidelines and must have the appropriate toxicity monitoring studies performed to be considered evaluable for dose limiting toxicity. Patients who do not have DLT and are not considered evaluable for dose limiting toxicity in Part A will be replaced.

11.2.2 Maximum Tolerated Dose:

- The MTD will be the maximum dose at which fewer than one-third of patients experience DLT (See [Section 5.5](#)) during Cycle 1 of therapy.
- In the unlikely event that two DLTs observed out of 6 evaluable patients are different classes of Adverse Effects (eg, hepatotoxicity and myelosuppression), AND all of the following conditions are met, expansion of the cohort to 12 patients will be considered:
 - One of the DLTs does not appear to be dose-related
 - The Adverse Effects are readily reversible
 - The study chair, PEP-CTN statistician, PEP-CTN committee chair or vice chair, and IND sponsor all agree that expansion of the cohort is acceptable

If fewer than 1/3 of patients in the expanded cohort experience dose-limiting toxicities, the dose escalation can proceed.

- The DLTs observed in the pharmacokinetic (PK) expansion cohort will contribute towards the total number of DLTs observed at the RP2D/MTD during the dose escalation portion of the

study. If $\geq 1/3$ of the cohort of patients at the RP2D/MTD (during the dose escalation plus the PK expansion) experience DLT then the MTD will be exceeded.

- If required number of responses per the Simon two-stage design for expansion is not met for either the ARMS or EWS phase 2 cohorts whilst the PK expansion is still enrolling, the PK expansion will subsequently be closed to those patients.

11.3 Dose Escalation and Determination of MTD

Rolling Six Design

The rolling six phase 1 trial design will be used for the conduct of this study.⁴⁰ Two to six patients can be concurrently enrolled onto a dose level, dependent upon (1) the number of patients enrolled at the current dose level, (2) the number of patients who have experienced DLT at the current dose level, and (3) the number of patients entered but with tolerability data pending at the current dose level. Accrual is suspended when a cohort of six has enrolled or when the study endpoints have been met.

Dose level assignment is based on the number of participants currently enrolled in the cohort, the number of DLTs observed, and the number of participants at risk for developing a DLT (i.e., participants enrolled but who are not yet assessable for toxicity). For example, when three participants are enrolled onto a dose cohort, if toxicity data is available for all three when the fourth participant entered and there are no DLTs, the dose is escalated and the fourth participant is enrolled to the subsequent dose level. If data is not yet available for one or more of the first three participants and no DLT has been observed, or if one DLT has been observed, the new participant is entered at the same dose level. Lastly, if two or more DLTs have been observed, the dose level is de-escalated. This process is repeated for participants five and six. In place of suspending accrual after every three participants, accrual is only suspended when a cohort of six is filled. When participants are inevaluable for toxicity, they are replaced with the next available participant if escalation or de-escalation rules have not been fulfilled at the time the next available participant is enrolled onto the study.

The following table provides the decision rules for enrolling a patient at (i) the current dose level (ii) at an escalated dose level, (iii) at a de-escalated dose level, or whether the study is suspended to accrual:

# Pts Enrolled	# Pts with DLT	# Pts without DLT	# Pts with Data Pending	Decision
2	0 or 1	0, 1 or 2	0, 1 or 2	Same dose level
2	2	0	0	De-escalate*
3	0	0, 1 or 2	1, 2 or 3	Same dose level
3	1	0, 1 or 2	0, 1 or 2	Same dose level
3	0	3	0	Escalate**
3	≥ 2	0 or 1	0 or 1	De-escalate*
4	0	0, 1, 2 or 3	1, 2, 3 or 4	Same dose level
4	1	0, 1, 2 or 3	0, 1, 2 or 3	Same dose level
4	0	4	0	Escalate**
4	≥ 2	0, 1 or 2	0, 1 or 2	De-escalate*
5	0	0, 1, 2, 3 or 4	1, 2, 3, 4 or 5	Same dose level
5	1	0, 1, 2, 3 or 4	0, 1, 2, 3 or 4	Same dose level
5	0	5	0	Escalate**
5	≥ 2	0, 1, 2 or 3	0, 1, 2 or 3	De-escalate*

THIS PROTOCOL IS FOR RESEARCH PURPOSES ONLY, SEE PAGE 1 FOR USAGE POLICY

6	0	0, 1, 2, 3, or 4	2, 3, 4, 5 or 6	Suspend
6	1	0, 1, 2, 3 or 4	0, 1, 2, 3 or 4	Suspend
6	0 or 1	5 or 6	0 or 1	Escalate**
6	≥ 2	0, 1, 2, 3 or 4	0, 1, 2, 3 or 4	De-escalate*

* If six patients already entered at next lower dose level, the MTD has been defined.

**If final dose level has been reached, the recommended dose has been reached.

If two or more of a cohort of up to six patients experience DLT at a given dose level, then the MTD has been exceeded and dose escalation will be stopped (see [Section 11.2.2](#) for exception to rule).

In addition to determination of the MTD, a descriptive summary of all toxicities will be reported.

